## Section 4: Statistical Principles

### Confidence intervals and P values

All analyses will be analyzed and reported as two-sided, done at a 5% significance level. Statistical tests will be conducted between the intensive weight loss and control group for the pre-defined primary and key secondary endpoints in a hierarchical manner. Thus gatekeeping procedure using serial testing will be applied to adjust for multiplicity among the key secondary outcomes. Formal statistical testing will be performed, in a prespecified sequence, as presented below, until one of the key secondary endpoints in the hierarchy fail to be statistically significant at  $\alpha=0.05$ . To limit the risk of type 1 errors we have selected only four endpoints to test - the primary endpoint and three key secondary endpoints. This procedure will preserve the “Family Wise Error Rate” of the

multiple analyses. The analyses will be performed in sequence until one of the analyses has failed to show the significant difference or all analyses have been completed at a significance level of 0.05. The sequence of the analyses for the selected secondary efficacy endpoints are listed as: (1) Change in body weight; (2) Change in serum urate; (3) Change in VAS Fatigue. (4) Change in VAS Pain.

### Analysis populations

Randomized trials are designed to address causal questions about options for care and thereby guide decisions by patients, clinicians, and other stakeholders. Thus, a rigorous trial should be analyzed according to the intention-to-treat principle, which require that patients assigned to a treatment strategy are kept in that group during the analysis, even if they deviate from their assigned treatment strategy after randomization. Primary analyses will be done on a modified ITT population, which include all randomized individuals who had the respective variable assessed at baseline.

## Section 5: Trial Population

### Screening

The number of individuals that have been screened for potential participation will be presented in the flow diagram (see draft figure 1 below).

### Eligibility

Inclusion criteria: Participants will be included if they are above 18 years AND have a Body Mass Index (BMI) of at least 30 kg/m^2 AND per expert opinion have gout AND meet the 2015 American College of Rheumatology/EULAR gout classification criteria, and with SU  $\geq 5$  mg/dL.

Exclusion criteria: Pregnant or breastfeeding. A history or suspicion of drug abuse within the past 5 years. Active muscle disease, cancer, previous kidney disease, and/or fatty liver. An estimated creatinine clearance  $<30$  mL/min calculated by the Cockcroft-Gault formula using ideal body weight. An investigational therapy within 8 weeks or 5 half-lives (whichever is longer) prior to the screening visit. Any other medical or psychological condition which, in the opinion of the investigator and/or medical monitor, might create undue risk to the patient or interfere with the

patient's ability to comply with the protocol requirements, or to complete the study. The number of included participants will be presented in the flow diagram (see figure 1).

#### Baseline patient characteristics

Patients will be described with respect to all variables shown in Table 1 in 'Proposed outline of tables and figures' below, separately for the two randomized groups. Data from the baseline visit will be used.

## Section 6: Analysis

### Outcome definitions

#### *Primary Outcome:*

Change in bodyweight (measured in kilograms) from baseline to the week 16 visit in the intention-to-treat (ITT) population.

#### *Key Secondary Outcomes:*

Change in SU at the final visit (16 weeks); Change in fatigue (VAS), and change in pain from their gout at their final visit (VAS).

#### *Other Secondary Outcomes:*

The proportion of participants reaching and maintaining target SU levels, defined as 8 weeks and 16 week visits with SU<6 mg/dL, respectively; the percentage reduction in SU at final visit (week 16); the proportion of individuals with any gout flare in the first-, and last 8 weeks following randomization, respectively; the number of gout flares during the trial period for each patient; functional status (HAQ); patient global (VAS); swollen joint count (SJC); tender joint count (TJC); change in number of tophi from baseline; and 36-Item Short Form Health Survey (SF-36: MCS and PCS apply).

### Analysis methods

For the primary and key secondary outcomes, we will use analysis of covariance (ANCOVA) modelled using repeated-measures mixed linear model analysis. Statistical tests inferring from P-values will be performed in sequence until one of the analyses has failed to show the significant difference or all analyses have been completed at a significance level of 0.05. The sequence of the analyses for the selected secondary efficacy endpoints are listed as: (1) Change in body weight; (2) Change in serum urate; (3) Change in VAS Fatigue. (4) Change in VAS Pain. The statistical model will include diet group (ID/CD) and time (in weeks) as fixed effects, and the interaction between time and diet group, with the respective variable (e.g. body weight at baseline) as covariate. Furthermore, the possible impact of the factors used for the stratified randomization will be explored, i.e. sex (M/ F), obesity class (<40/≥40 kg/m^2), and SU level (< 6/≥6 mg/dL) but will not be considered part of the primary model. We aim to assess whether data provide evidence of superiority of ID to CD group (primary objective). Thus, the null hypothesis is no difference

between treatments at endpoint (week 16). Response variables and adverse events (binary outcomes) will be analyzed by comparing the proportions responding in each group with the Risk Difference (and 95% CI's), with no further adjustments for covariates.

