However, in view of the use of a formula (liquid) low energy diet in the intensive weight loss group, as well as more attention provided from the dietitians, blinding of staff or participants will not be feasible. As a consequence, the possible influence of performance bias on patient-reported outcomes will be discussed as a possible limitation.

Statistical methods

Data will be analysed according to a pre-established statistical analysis plan (SAP). Primary analyses will be done on a modified ITT population, which include all randomised individuals who had the respective variable assessed at baseline. All analyses will be analysed and reported as two-sided, done at a 5% significance level.

We will use analysis of covariance (ANCOVA) for the continuous outcome measures modelled using repeated-measures (mixed linear model) analysis. The statistical model will include diet group (ID/CD) as fixed effects, an interaction between time and diet group, and the respective variable (e.g. body weight at baseline) as assessed at randomisation as covariate. Furthermore, the possible impact on the effect size of the factors used for the stratified randomisation will be explored, i.e. sex (M/ F), obesity class ($<40/\geq40$ kg/m 2), and SU level ($< 6/\geq6$ mg/dL). We aim to assess whether data provide evidence of superiority of ID to CD group (primary objective). Thus, the primary null hypothesis is no difference between treatments at endpoint (week 16). Response variables (binary outcomes; e.g. the proportion of patients losing more than 5% of baseline weight) will be analysed with a logistic regression model, including the same fixed effects (covariates) as for the analyses of continuous outcomes.

Data monitoring

Careful conduct of the clinical trial according to this protocol has a major impact on the credibility of the results. Careful monitoring will ensure that difficulties are noticed early and their occurrence or recurrence minimised. There are two distinct types of monitoring that generally characterise RCTs: (1) The oversight of the quality of the trial, while the other type involves (2) Breaking the blinding to make treatment comparisons (that is, interim analysis). Both types of trial monitoring, in addition to entailing different staff responsibilities, involve access to different types of trial data and information, and thus different principles apply for the control of potential statistical and operational bias.

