## Power and sample size

Using SAS Power and Sample Size (Copyright © 2013 by SAS Institute Inc., Cary, NC, USA) it was calculated assuming that the standard deviation (SD) of weight change at week 16 would be 6.0 kg, that, 60 patients (30 in each group) would provide 89% confidence (power=0.888) to detect a clinically relevant 5 kg difference (p=0.05, two-sided) in mean bodyweight change between individuals allocated to intensive or conventional diet. If a drop-out rate of up to 20% (i.e., 6 patients in each group) is assumed, the trial will still have an acceptable power (>0.80) to detect a 5 kg difference between the groups.

Among the key secondary outcome measures is the mean change in SU at the final visit: Assuming a common SD of 1.6 mg/dL, a total sample size of 60 gout patients (randomized 1:1) will have a sufficient statistical power (81.5%) to detect a mean difference of 1.2 mg/dL. Patient-Reported Outcome Measures (PROMs; e.g. VAS-Pain and VAS-fatigue): With 60 patients in total, the trial will have sufficient power to detect a statistically significant effect size (i.e. standardized mean difference [SMD]) corresponding to a large clinical effect (SMD=0.8; power=86.1%).

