### Missing data

Missing data will be handled implicitly by the mixed model for the main analyses (Table 2). Incomplete outcome data, for example, caused by patients missing some visits or dropping out of the study, are common in longitudinal studies. Mixed models assume that the missingness is independent of unobserved measurements, but dependent on the observed measurements. This assumption is called “*Missing At Random*” (MAR) and is often reasonable. Using mixed models, valid estimates of treatment effects will be obtained even when the missing values are not completely random (“*Missing Completely At Random*”, [MCAR]) and additional methods for handling missing data, such as multiple imputation, are generally not required.

Missing data have until recently, seriously compromised inferences from clinical trials. For example, editorials in the New England Journal of Medicine have noted how missing data have limited the ability to draw definitive conclusions from weight-loss trials. Analyses that are performed with methods such as repeated measures mixed models often assume that missing data are missing at random (MAR), and such an assumption often makes sense for the primary analyses. However, the observed data can never verify whether this assumption is correct. Therefore, we will assess robustness by using sensitivity analyses, noting that explicit use and reporting of sensitivity analyses is a novel area in trial research; i.e. the interpretation of the collective results from a sensitivity analysis when some of the analyses are in opposition to the primary analysis are not without controversies. However, we will assess the robustness of inferences (from our primary analyses) about treatment effects to various missing-data assumptions by conducting sensitivity analyses that relates inferences to one or more parameters that capture departures from the primary missing data assumption.

Sensitivity analyses should be easy to interpret by clinicians. We will apply the framework suggested by White et al, published in the British Medical Journal (2011) for intention to treat analysis that depends on making plausible assumptions about the missing data and including all participants in sensitivity analyses:

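### The mixed model uses one baseline slope for both week 8 and week 16, so its validity under missing-at-random drop-out also rests on an unstated equal-slope assumption

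*SAP*

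**What the plan says.** SAP, Section 6, Analysis methods, gives the model fixed effects for diet and for time, counted in weeks. The remaining terms are described thus: "and the interaction between time and diet group, with the respective variable (e.g. body weight at baseline) as covariate". The Protocol (Statistical methods) has the same baseline structure: "an interaction between time and diet group, and the respective variable (e.g. body weight at baseline) as assessed at randomisation as covariate". Neither document lists a baseline-by-time term, names a covariance structure, or says whether time is categorical. The null hypothesis concerns week 16, and the four outcomes tested in sequence (weight, serum urate, VAS fatigue, VAS pain) all use this model.

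SAP, Missing data, relies on the same model for incomplete data: "Using mixed models, valid estimates of treatment effects will be obtained even when the missing values are not completely random". It adds that further methods such as multiple imputation are generally not needed. Three appendix tables follow. Table 1 refits the mixed model after baseline observation carried forward (BOCF). Table 2 uses two-sample t-tests in participants complete on all four outcomes. Table 3 adds the stratification factors to the primary model, with a footnote that also specifies BOCF.

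**The concern.** A single baseline coefficient means that a 1-unit higher baseline is taken to predict the same difference in outcome at week 8 as at week 16. There is no stated reason to expect that. The intensive diet changes phase at week 8, concomitant therapy is unrestricted, and pain and fatigue scores may fluctuate with flares. If the slopes differ, the fitted slope is a compromise, and the week-16 contrast is adjusted with a value that is not the week-16 slope.

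Two things are at stake. The first is precision at week 16. The second is the missing-data argument: likelihood-based estimates are valid under missing at random (MAR) only if the mean model is also right. Drop-out that depends on observed baseline is MAR, yet if it depends on baseline differently by arm, the arms' completers differ in baseline and a wrong slope corrects that difference wrongly. Differential drop-out is not far-fetched. The intensive arm has weekly sessions and the control arm three in all, and the Protocol itself says that lack of blinding may affect the risk of drop-out.

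**Working it through.** **The plan's own figure.** With a 5 kg difference, SD 6.0 kg ("assuming that the standard deviation (SD) of weight change at week 16 would be 6.0 kg"), 30 per arm and two-sided 0.05, the noncentrality is 5 / (6.0 × √(2/30)) = 3.23 on 58 df. Power is 0.8876, against 0.888 stated. The other stated powers also reproduce: 0.807 with 24 per arm (stated as above 0.80), 0.815 for serum urate and 0.861 for SMD 0.8. They rest on unadjusted t-tests, so this point does not touch them.

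**Assumptions.** The documents give no baseline slopes, so all slopes, residual SDs and drop-out models below are assumed, as is an unstructured covariance. For urate: 30 per arm, true difference −1.2 mg/dL, baseline SD 1.6, residual correlation 0.6.
- (a) slopes 0.8 (week 8) and 0.5 (week 16), residual SD 0.9 and 1.3
- (b) slopes 0.7 and 0.5, residual SD 1.1 and 1.2

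**Precision, complete data.** The common slope is b = (w8·b8 + w16·b16) / (w8 + w16), with w8 = σ16² − ρσ8σ16 and w16 = σ8² − ρσ8σ16. The variance of the contrast is (2/n)·[σ16² + (b − b16)²·Var(baseline)].
- (a) w8 = 1.69 − 0.702 = 0.988 and w16 = 0.81 − 0.702 = 0.108, so b = 0.77. Variance ratio: 1 + 0.27² × 2.56 / 1.69 = 1.11. SE about 5% larger (0.354 against 0.336).
- (b) w8 = 1.44 − 0.792 = 0.648 and w16 = 1.21 − 0.792 = 0.418, so b = 0.62. Variance ratio: 1 + 0.12² × 2.56 / 1.44 = 1.03. SE about 1.3% larger.

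Simulation gives about 5% in (a) and 0-1.5% in (b).

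**Bias under MAR drop-out.** Take about 22% drop-out after week 8, with log-odds 1.0 per SD of baseline. Where high-baseline controls leave, the remaining controls average about 0.19 SD, or 0.19 × 1.6 = 0.30 mg/dL, lower at baseline. The slope error times this shift is 0.27 × 0.30 = 0.08 in (a) and 0.12 × 0.30 = 0.04 in (b). Simulated estimates (drop-out about 21-24%) are a little further from −1.2, because refitting the covariance under the restriction pulls the slope closer to week 8 (about 0.78 in (a)):

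| Drop-out depends on baseline | (a) | (b) |
|---|---|---|
| Control only, high baseline leaves | −1.29 to −1.31 | −1.25 to −1.27 |
| Control only, low baseline leaves | −1.11 to −1.12 | −1.15 |
| Opposite directions by arm | −1.38 to −1.40 | −1.31 to −1.32 |
| Opposite directions, reversed | −1.01 | −1.08 |
| Same in both arms | −1.20 | −1.20 |

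With baseline-by-visit added, the estimates are −1.19 to −1.22. The SE with drop-out is about 0.34-0.41. Coverage is 94-96% for control-only dependence and 92-93% for opposite dependence in (a).

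**Body weight.** The only clues are earlier mean losses of about 11% at 8 weeks (Protocol, Interventions) and about 12% at 16 weeks (SAP, Background and rationale). Read as loss proportional to baseline, which is an assumption, they give slopes of change of −0.11 and −0.12. Assume baseline SD 20 kg, week-8 SD 4.5 kg and residual correlation 0.8. The common slope is then about −0.108, and the residual variance at week 16 is 36 − 0.12² × 400 = 30.2. The variance loss is 0.012² × 400 / 30.2, about 0.2%. Simulated SE is 1.42 as planned and 1.43 with the extra term, power is 0.931 for both, and bias with 20% drop-out is about 0.1 kg or less on 5 kg.

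Material bias needs a wider gap. Slopes −0.05/−0.12 give about −0.3 kg (control only) and −0.6 kg (opposite, coverage 93.5%). Slopes 0/−0.15 give −0.6 and −1.15 kg (opposite coverage 89%). With −0.12/−0.05 the sign turns: +0.5 kg (opposite).

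**The case against.** A reader might infer that the week-16 contrast is adjusted with the wrong slope, loses precision and is biased. The documents do not support that as fact. All three need slopes that differ between visits, and no slope is given. With complete data, randomisation keeps the contrast unbiased whatever the slopes. Drop-out that depends on baseline alike in both arms leaves no bias either. It would also be wrong to say that the estimates are inflated: the sign depends on who leaves which arm and on which slope is steeper. The pull of the slope towards week 8 presumes an unstructured covariance and a smaller week-8 residual variance, neither of which the SAP states.

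The sensitivity analyses need a fair reading as well. Appendix Tables 1 and 3 keep the single slope, but BOCF leaves no missing outcomes, so only the precision point applies there (BOCF has its own, separate bias). Appendix Table 2 has no baseline slope at all, so it escapes the restriction, but it drops baseline adjustment and needs data missing completely at random.

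All of this stands, and it makes the point conditional and modest. It does not remove it: no planned analysis both frees the slope and keeps baseline adjustment under MAR. The weight figures are mean losses from earlier studies and say nothing about urate, fatigue or pain.

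**Conclusion.** The point holds as a specification gap with conditional consequences. As written, the model imposes equal baseline slopes at weeks 8 and 16, and the SAP's claim of validity under MAR depends on that without saying so. Under the assumed urate slopes the cost is about 0-5% in SE. For control-only dependence the bias is at most about a quarter of the SE. It reaches about half only with strong, opposite dependence in the two arms, which nothing in the documents indicates. For body weight, the primary outcome, the effect is probably negligible unless the slopes lie much further apart than the documents' figures suggest. These sizes rest on assumed slopes, variances and drop-out models. The case for acting is that the change costs almost nothing and removes an assumption behind all four formal tests.

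**What to change.** Before SAP approval, in SAP Section 6 (Analysis methods), enter visit as a categorical factor (week 8, week 16) and add baseline value-by-visit to the model for the continuous outcomes. Carry the same terms into the models behind Appendix Tables 1 and 3. Name the covariance structure in the same sentence. Keep the week-16 diet difference as the estimate and the test. With only two post-baseline visits, categorical and linear time describe the same means, so the categorical wording only removes ambiguity; the interaction is the substantive change. The cost is one term and one degree of freedom, with no new data. Where slopes are nearly equal the loss is negligible (SE 1.43 against 1.42 in the weight example). Adding the term after the data are seen would be post hoc, so the timing matters.

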## Randomization

After baseline measurements, the participants were randomized to either Intensive Diet (ID) or Conventional Diet (CD) group. A computer-generated randomization sequence was produced, before any participants were enrolled, allocating participants in permuted blocks of 2 to 4 to the ID or the CD group (1:1). The randomization sequence was prepared using SAS Proc Plan; after the list was generated it was concealed in a password-protected computer file only accessible by the data manager. Randomization was stratified according to sex (M vs F), baseline obesity class (<40 vs.  $\geq 40$  kg/m^2), and SU level (< 6 vs.  $\geq 6$  mg/dL). These eight mutually independent randomization sequences (each including 60 “virtual patients”) was entered into the eCRF by the data manager ([name]).

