1. We did our best to follow up all randomized participants, even if they withdrew from their allocated treatment (i.e. real data is better than statistical imputation strategies).
2. We will perform a main analysis of all observed data that are valid under a plausible assumption about the missing data by using repeated measures mixed linear models (valid assuming that data is '*Missing At Random*'); See Table 2.
3. We will perform sensitivity analyses to explore the effect of departures from the assumption made in the main analysis; see SAP-Appendix Tables 1 and 2.

4. We will account for all randomized participants, also in the sensitivity analyses:

- We will apply a “non-responder imputation techniques” for the missing data (using BOCF) in the analyses provided in SAP-Appendix Table 1 (potentially valid even if data is '*Not Missing At Random*' [NMAR]).
- We will apply a naïve approach where we only perform our analyses on the data set where participants with missing data is excluded; i.e. participants with complete data for all of the four outcomes while still respecting the original treatment allocation (i.e. valid assuming data is Missing Completely at Random; MCAR), and using simple two-sample t-tests; see SAP-Appendix Tables 2.

If the treatment effect is qualitatively maintained for the range of offsets that are clinically plausible, then the findings will be considered robust. Extensions apply the offsets to means adjusted for available covariates (e.g. stratifying factors).

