| Other secondary outcomes | On treatment target, n(%)*          |              |              |                       | n.a.    |
|                          | Serum urate reduction, %            |              |              |                       | n.a.    |
|                          | VAS patient global                  |              |              |                       | n.a.    |
|                          | HAQ                                 |              |              |                       | n.a.    |
|                          | Swollen joint count                 |              |              |                       | n.a.    |
|                          | Tender joint count                  |              |              |                       | n.a.    |
|                          | Palpable tophi                      |              |              |                       | n.a.    |
|                          | SF-36 MCS                           |              |              |                       | n.a.    |
|                          | SF-36 PCS                           |              |              |                       | n.a.    |

Abbreviations: ID - Intensive diet, CD – conventional diet.

1: Continuous outcome estimates will be derived from the repeated measures linear mixed models where missing data in the ITT population is handled implicitly; the inference will be provided as the difference between least squares means with 95 CI's around them.

2: Dichotomous outcomes will be reported directly as observed (no imputations); the inference will be provided (unadjusted as the difference between proportions, i.e. Risk Difference, with 95% confidence interval).

\*Defined as having a serum urate < 6.0 mg/dL at both week 8 *AND* week 16

**Table 3:** Adverse events and harms

| Event                              | ID
(n=XX) | CD
(n=XX) | Difference (95%CI) |
|------------------------------------|--------------|--------------|--------------------|
| Self-reported flare, 0-16 weeks    |              |              |                    |
| First 8 weeks (0-8)                |              |              |                    |
| Last 8 weeks (8-16)                |              |              |                    |
| Other                              |              |              |                    |
| Serious Adverse Events, 0-16 weeks |              |              |                    |

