### Change from baseline

|                               | Outcome            | ID
(n=XX) | CD
(n=XX) | Difference (95%CI) | P-
value |
|-------------------------------|--------------------|--------------|--------------|--------------------|-------------|
| Primary outcome        | Weight loss, kg    |              |              |                    |             |
| Key secondary outcomes | Serum urate, mg/dL |              |              |                    |             |
|                               | VAS fatigue        |              |              |                    |             |
|                               | VAS pain gout      |              |              |                    |             |

Values are least squares means (SE), unless otherwise stated. Abbreviations: ID – intensive diet, CD – conventional diet.

1: Continuous outcome estimates will be derived from the repeated measures linear mixed models where missing data in the ITT population is handled explicitly with a non-responder imputation (i.e. baseline observation carried forward; indicative of a possible NMAR issue); the inference will be provided as the difference between least squares means with 95% CI's around them.

**SAP-Appendix Table 2:** Changes in primary and key secondary endpoints (using 2-sample t-tests)

|                               |                    | Change from baseline  |              |                    |         |
|-------------------------------|--------------------|-----------------------------------|--------------|--------------------|---------|
|                               | Outcome            | ID
(n=XX)                      | CD
(n=XX) | Difference (95%CI) | P-value |
| Primary outcome        | Weight loss, kg    |                                   |              |                    |         |
| Key secondary outcomes | Serum urate, mg/dL |                                   |              |                    |         |
|                               | VAS fatigue        |                                   |              |                    |         |
|                               | VAS pain gout      |                                   |              |                    |         |

Values are means (SD). Abbreviations: ID – intensive diet, CD – conventional diet.

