1: Continuous outcomes estimates will be derived from descriptive statistics and 2-sample t-tests (change from baseline at 16 weeks) where missing data is handled explicitly by excluding participants with missing data for any of the four outcomes while still respecting the original treatment allocation (i.e. valid assuming data is missing completely at random); the inference will be provided as the difference group means with 95% CI's around them.

**SAP-Appendix Table 3:** Changes in primary and key secondary endpoints (adjusted for the three stratifying factors)\*

|                               |                    | Change from baseline  |              |                    |         |
|-------------------------------|--------------------|-----------------------------------|--------------|--------------------|---------|
|                               | Outcome            | ID
(n=XX)                      | CD
(n=XX) | Difference (95%CI) | P-value |
| Primary outcome        | Weight loss, kg    |                                   |              |                    |         |
| Key secondary outcomes | Serum urate, mg/dL |                                   |              |                    |         |
|                               | VAS fatigue        |                                   |              |                    |         |
|                               | VAS pain gout      |                                   |              |                    |         |

Values are least squares means (SE), unless otherwise stated. Abbreviations: ID – intensive diet, CD – conventional diet.

\*Based on the same statistical model as the primary analyses (Table 2); adding three further covariates corresponding to the stratified analysis.

1: Continuous outcome estimates will be derived from the repeated measures linear mixed models where missing data in the ITT population is handled explicitly with a non-responder imputation (i.e. baseline observation carried forward); the inference will be provided as the difference between least squares means with 95% CI's around them.

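### The gatekept models omit the three stratification factors, and the one table that adjusts for them gives conflicting notes on missing data

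*SAP*

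**What the plan says.** - **Design.** SAP Section 3 (Randomization): "Randomization was stratified according to sex (M vs F), baseline obesity class" and SU level, giving eight separate sequences.
- **Gatekept models.** SAP Section 6 (Analysis methods) fits a repeated-measures mixed model with group, time, their interaction and the baseline value of the outcome. The stratification factors are to be explored "but will not be considered part of the primary model". The protocol (Statistical methods) likewise only explores them.
- **Missing data in the main analysis.** SAP Table 2, footnote 1: "missing data in the ITT population is handled implicitly".
- **Missing-data sensitivity analyses.** SAP Section 6 (Missing data), item 3, plans analyses of "departures from the assumption made in the main analysis; see SAP-Appendix Tables 1 and 2". Item 4 assigns BOCF to Appendix Table 1. The closing sentence of that section speaks of extending the offsets to covariate-adjusted means, with the stratifying factors as an example, but names no table.
- **Appendix Table 3.** The asterisk note reads "Based on the same statistical model as the primary analyses (Table 2); adding three further covariates corresponding to the stratified analysis". Footnote 1 of the same table says missing data are "handled explicitly with a non-responder imputation (i.e. baseline observation carried forward"). No text in the SAP body cites this table.

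**The concern.** Stratified blocks balance the arms on the three factors. If the factors predict the outcome beyond the baseline covariate, a model without them keeps their variance in the residual. The standard error is then too large for the design, the test is conservative and the intervals are wider than necessary. Sex is in none of the four models, and the two VAS models carry no stratum information by design.

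Appendix Table 3 is where a reader would look to see what adjustment does. Its asterisk note points to Table 2, where missing data are left to the mixed model, while its footnote imputes baseline values. Two analysts following this SAP could produce two different tables. Under the BOCF reading, a gap between Table 3 and Table 2 would reflect mainly the imputation, in a table presented as the adjusted version of the primary analysis.

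**Working it through.** **The plan's own figures.** Inputs from SAP Section 3 (Power and sample size), two-sided alpha 0.05. Two-sample t-test power uses the noncentral t with noncentrality δ / (σ√(2/n)).

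- Weight, 30 per arm: 5 / (6.0 × √(2/30)) = 3.23, 58 df, power 0.888 (stated 0.888).
- Weight, 24 per arm after 20% dropout: 0.807 (stated above 0.80).
- SU: 1.2 / (1.6 × √(2/30)) = 2.90, power 0.815 (stated 81.5%).
- Patient-reported outcomes, standardised difference 0.8: 0.861 (stated 86.1%).

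All reproduce.

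**Part 1: factors left out.** Let R² be the share of residual variance the factors explain beyond the baseline covariate. The documents do not give it, so a range is shown. With perfect balance, the type I error of the model without the factors is 2[1 − Φ(1.96/√(1−R²))]. Real blocks balance less than perfectly, so two separately written simulations (A: 40,000 runs per scenario; B: 20,000) were also run.

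| Assumed R² | 0% | 5% | 10% | 20% |
|---|---|---|---|---|
| Type I error, formula (%) | 5.0 | 4.4 | 3.9 | 2.8 |
| Type I error, A, no dropout (%) | 5.1 | 4.6 | 4.3 | 3.3 |
| Type I error, B, no dropout (%) | 5.1 | 4.4 | 4.2 | 3.1 |
| Type I error, B, 20% dropout (%) | 4.7 | 4.8 | 4.5 | 3.5 |
| Power change from adjusting, A (points) | -0.4 | +0.9 | +1.8 | +3.8 |
| Power change from adjusting, B (points) | -0.4 | +0.8 | +2.0 | +3.6 |
| Power change, B, 20% dropout (points) | -0.4 | +0.9 | +2.4 | +4.9 |

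Assumptions in B: 60 patients; eight strata; random blocks of 2 or 4; SD 6 kg at weeks 8 and 16 with correlation 0.7; 20% female, 25% with BMI ≥40 and 35% with SU <6; factors equally prognostic and independent of the baseline covariate; dropout completely at random, half of it before week 8. The SAP names neither a covariance structure nor a degrees-of-freedom method; unstructured and Satterthwaite were assumed. Monte Carlo standard error is about 0.15 points for type I error and 0.2 to 0.3 for power.

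**Part 2: two readings of Appendix Table 3.** BOCF sets the change to zero at missed visits, so the expected difference is

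ID loss × (1 − ID dropout) − CD loss × (1 − CD dropout).

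With the SAP's 20% dropout in each arm and assumed mean losses of 12 and 7 kg: 12 × 0.8 − 7 × 0.8 = 9.6 − 5.6 = 4.0 kg, against 5.0 kg for the mixed model. Using model B with R² = 10% and 8,000 runs (Monte Carlo standard error up to 0.55 points):

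| Table | Missing data | Factors | Expected difference | Chance of p<0.05 |
|---|---|---|---|---|
| Table 2 | implicit | no | 5.0 kg | 82.8% |
| Appendix Table 1 | BOCF | no | 4.0 kg | 62.5% |
| Appendix Table 3, per footnote 1 | BOCF | yes | 4.0 kg | 63.8% |
| Appendix Table 3, per asterisk note | implicit | yes | 5.0 kg | 84.9% |

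Closed-form check of the second row: the BOCF variance per arm is (1−d) × 36 + d(1−d) × loss². This gives 28.8 + 0.16 × 144 = 51.84 for ID and 28.8 + 0.16 × 49 = 36.64 for CD. The standard error is √((51.84 + 36.64)/30) = 1.72, and the power is Φ(4.0/1.72 − 1.96) = 0.644, close to the simulated value.

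Within one simulated trial:

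- Table 3 as footnoted minus Table 2 averages -1.0 kg (SD 1.2).
- Table 3 as footnoted minus Appendix Table 1 averages 0.0 (SD 0.2).
- Table 3 per the asterisk note minus Table 2 averages 0.0 (SD 0.3).

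The choice of reading moves the chance of p<0.05 by 84.9 − 63.8 = 21.1 points; adjustment moves it by 63.8 − 62.5 = 1.3 or 84.9 − 82.8 = 2.1 points. With assumed losses of 8 and 3 kg the two readings give 85.2% and 74.8%, a gap of 10.4 points.

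The BOCF difference also depends on how dropout splits. With 10% in each arm it is 12 × 0.9 − 7 × 0.9 = 4.5 kg. With 30% in ID and 10% in CD it is 12 × 0.7 − 7 × 0.9 = 2.1 kg (2.9 kg at losses of 8 and 3). Reversed, it is 12 × 0.9 − 7 × 0.7 = 5.9 kg (5.1 kg at losses of 8 and 3).

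**The case against.** On part 1, protocol and SAP agree, the exclusion is openly prespecified, and an adjusted table is planned. The size rests on an R² the documents do not give. Baseline weight and baseline SU overlap with two of the three strata, so for the first two tests in the hierarchy the gain is probably at the low end, where adjustment changes power by -0.4 to +0.9 points. Adding the factors now would depart from the protocol model in an open-label trial whose SAP already describes conduct in the past tense. All of this stands. It makes part 1 a question of efficiency, not an error, and it is why the change must be documented.

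On part 2, the asterisk note speaks of the statistical model and footnote 1 of missing data, so both could hold: the same model, fitted to BOCF data. Appendix Table 1 already fits mixed models to BOCF data, and the step from Appendix Table 1 to Table 3 would then show the effect of adjustment. That reading is possible. But the Missing data section does not list Table 3 among its sensitivity analyses, and the adjustment would be shown only under BOCF. No adjusted analysis comparable with the primary one would remain. It is also true that no gatekept decision depends on an appendix table, and that the 21-point gap is specific to the 12 and 7 kg assumption.

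**Conclusion.** Both parts hold, and the point is minor. Leaving the factors out causes no bias and no inflation of type I error; at most it forgoes some precision that the stratified design offers. Part 2 is the firmer finding. The SAP does not settle which analysis Appendix Table 3 contains, and the two readings differ by an expected 1.0 kg at 20% equal dropout and a true difference of 5 kg. That kilogram follows from the BOCF arithmetic for any pair of mean losses 5 kg apart. The gap in the chance of p<0.05 (about 10 to 21 points) depends on the assumed losses and on dropout at random.

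**What to change.** (a) Whichever model is primary, change footnote 1 of Appendix Table 3 so that missing data are handled as in Table 2, and cite the table under Analysis methods or Missing data. If a BOCF version with the factors is also wanted, present it separately as the adjusted counterpart of Appendix Table 1. Cost: one footnote and one citation.

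(b) Under Analysis methods, enter sex, obesity class and SU stratum as main effects in the primary and key secondary models, and state that a factor with no variation in the analysed data is dropped. Keep the model without the factors as the sensitivity table. Record this as a departure from the protocol's model before SAP approval and final analysis (SAP Section 3, Timing of final analysis). Cost: up to 3 degrees of freedom, about 0.3 to 0.6 points of power if the factors explain nothing, Table 2 and Figure 2 drawn from the adjusted model, and a late, documented model change. No new data are needed.

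If the sponsor keeps the model without the factors as primary, (a) is still needed.
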